### **8.3.2. Method of Detecting AEs and SAEs**

The method of recording, evaluating, and assessing causality of AEs and SAEs and the procedures for completing and transmitting SAE reports are provided in [Appendix 3](#).

Care will be taken not to introduce bias when detecting AEs and/or SAEs. Open-ended and nonleading verbal questioning of the participant is the preferred method to inquire about AE occurrences.

### **8.3.3. Follow-up of AEs and SAEs**

After the initial AE/SAE report, the investigator is required to proactively follow each participant at subsequent visits/contacts. For each event, the investigator must pursue and obtain adequate information until resolution, stabilization, the event is otherwise explained, or the participant is lost to follow-up (as defined in [Section 7.3](#)).

In general, follow-up information will include a description of the event in sufficient detail to allow for a complete medical assessment of the case and independent determination of possible causality. Any information relevant to the event, such as concomitant medications and illnesses, must be provided. In the case of a participant death, a summary of available autopsy findings must be submitted as soon as possible to Pfizer Safety.

Further information on follow-up procedures is given in [Appendix 3](#).

### **8.3.4. Regulatory Reporting Requirements for SAEs**

Prompt notification by the investigator to the sponsor of an SAE is essential so that legal obligations and ethical responsibilities towards the safety of participants and the safety of a study intervention under clinical investigation are met.

The sponsor has a legal responsibility to notify both the local regulatory authority and other regulatory agencies about the safety of a study intervention under clinical investigation. The sponsor will comply with country-specific regulatory requirements relating to safety reporting to the regulatory authority, institutional review boards (IRBs)/ethics committees (ECs), and investigators.

Investigator safety reports must be prepared for suspected unexpected serious adverse reactions (SUSARs) according to local regulatory requirements and sponsor policy and forwarded to investigators as necessary.

An investigator who receives an investigator safety report describing an SAE or other specific safety information (eg, summary or listing of SAEs) from the sponsor will review and then file it along with the investigator's brochure and will notify the IRB/EC, if appropriate according to local requirements.

### **8.3.5. Exposure During Pregnancy or Breastfeeding, and Occupational Exposure**

Exposure to the investigational product under study during pregnancy or breastfeeding and occupational exposure are reportable to Pfizer Safety within 24 hours of investigator awareness.

#### **8.3.5.1. Exposure During Pregnancy**

Details of all pregnancies in female participants and, if indicated, female partners of male participants will be collected after the start of study intervention and until approximately 130 days that is at least 5 terminal half-lives after the last dose.

If a pregnancy is reported, the investigator should inform the sponsor within 24 hours of learning of the pregnancy and should follow the procedures outlined in [Appendix 4](#).

Abnormal pregnancy outcomes (eg, spontaneous abortion, fetal death, stillbirth, congenital anomalies, ectopic pregnancy) are considered SAEs.

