		
Section 8.4:
 
 
Overdose updated based on updated PK/PD simulation results and NOAEL from 6-month monkey toxicology study. Definition of overdose for this study was redefined based on operational considerations.
 
 
Sections 8.5, 8.6 and 8.9:
 
 
Updated per updated protocol template text.
 
Section 8.6 updated per SOA.
 
 
Section 8.8.1:
 
 
Updated Prep B2 and Prep 1.5 sample descriptions for clarity.
 
 
Appendix 10.4:
 
 
Updated contraception requirements per emerging PK data from C3651001.
 
 
Updated protocol to include PACL items:
 
 
A pre-dose PK sample will also be collected on Day 1 in addition to the post-dose PK sample.
 
Radiation as primary SOC is not permitted (allowed for metastases for palliative care)
 
Inclusion Criterion # 6-Paclitaxel or nab-paclitaxel is permitted as an allowable therapy. Therefore, the allowable therapies are a platin + pemetrexed <math>\pm</math> pembrolizumab or a platin + nab paclitaxel or paclitaxel <math>\pm</math> pembrolizumab as first or second line therapy.
 

Original protocol	27 November 2019	Not applicable (N/A)

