Therefore, it is hypothesized that cachexia in many types of cancer, including NSCLC, pancreatic cancer, and colorectal cancer, is largely mediated via GDF-15 and that suppression of GDF-15 in these patients may lead to improvement in serious aspects of cachexia such as anorexia leading to unintended weight loss, fatigue and impaired mobility. Furthermore, given the observations of GDF-15 elevation with platinum therapy, patients receiving standard of care anti-tumor treatment that includes systemic platinum-based therapy, may be a specific population that could potentially gather additional benefit from GDF-15 inhibition.

Study C3651009 represents the first administration of PF-06946860 in patients with cancer and cachexia. As such, an open-label design and a small sample size have been implemented in order to transparently establish an initial assessment of clinical safety, PK, PD and immunogenicity of this novel therapy.

A treatment duration of 12 weeks is consistent with available pre-clinical toxicology coverage and to support development of PF-06946860 in subsequent Phase 2 studies. A treatment duration of 12 weeks should provide sufficient safety information to inform subsequent PF-06946860 Phase 2 studies. After the 12-week treatment period, participants will be followed up for 12 weeks post last dose. Based on the preliminary population PK/PD simulation results, it is anticipated that at 12 weeks post last dose of **CCI** PF-06946860 the unbound PF-06946860 concentrations will be below the level that would be expected to fully suppress GDF-15.

PF-06946860 will be dosed via subcutaneous injections, every 3 weeks. However, the dosing frequency in Cohort 2 may be adjusted based upon emerging data from Cohort 1.

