**CCI**

The baseline assessments for the CT scan-derived LSMI, **CCI** and PROs will be performed during the screening period, but do not need to be reviewed to determine eligibility.

PF-06946860 dosing can be initiated at the start of a participant's first or second cycle of standard of care anti-tumor therapy. Flexibility in the initiation of PF-06946860 is intended to minimize any interference with the evaluation, diagnosis, and/or initiation of standard of care anti-tumor therapy.

At the present time, embryo-fetal developmental toxicology studies with PF-06946860 have not been conducted. Consequently, to prevent pregnancy, the protocol includes contraceptive provisions for both male and female participants (see [Section 5.3.1](#) and [Appendix 4 Section 10.4.4](#)).

[figure not shown]
Banked biospecimens will be collected for exploratory pharmacogenomic/genomic/biomarker analyses and retained in the Biospecimen Banking System (BBS), which makes it possible to better understand the investigational product's mechanism of action and to seek explanations for differences in, for example, exposure, tolerability, safety, and/or efficacy not anticipated prior to the beginning of the study.

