## **10.4. Appendix 4: Contraceptive Guidance and Collection of Pregnancy Information**

### **10.4.1. Male Participant Reproductive Inclusion Criteria**

Male participants are eligible to participate if they agree to the following requirements during the intervention period and for at least 22 weeks after the last dose of study intervention, which corresponds to the time needed to eliminate study intervention(s):

- Refrain from donating sperm.

PLUS either:

- Be abstinent from heterosexual intercourse with a female of childbearing potential as their preferred and usual lifestyle (abstinent on a long-term and persistent basis) and agree to remain abstinent.

OR

- Must agree to use a male condom when engaging in any activity that allows for passage of ejaculate to another person.

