### **10.4.2. Female Participant Reproductive Inclusion Criteria**

A female participant is eligible to participate if she is not pregnant or breastfeeding, and at least 1 of the following conditions applies:

- Is not a WOCBP (see definitions below in [Section 10.4.3](#)).

OR

- Is a WOCBP and using a contraceptive method that is highly effective (with a failure rate of <1% per year), as described below, during the intervention period and for at least 22 weeks after the last dose of study intervention, which corresponds to the time needed to eliminate any study intervention(s). The investigator should evaluate the effectiveness of the contraceptive method in relationship to the first dose of study intervention.

The investigator is responsible for review of medical history, menstrual history, and recent sexual activity to decrease the risk for inclusion of a woman with an early undetected pregnancy.

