## Collection of Pregnancy Information

For both unapproved/unlicensed products and for marketed products, an exposure during pregnancy (EDP) occurs if:

- A female becomes, or is found to be, pregnant either while receiving or having been exposed (eg, because of treatment or environmental exposure) to the investigational product; or the female becomes or is found to be pregnant after discontinuing and/or being exposed to the investigational product;
- An example of environmental exposure would be a case involving direct contact with a Pfizer product in a pregnant woman (eg, a nurse reports that she is pregnant and has been exposed to chemotherapeutic products).
- A male has been exposed (eg, because of treatment or environmental exposure) to the investigational product prior to or around the time of conception and/or is exposed during his partner's pregnancy.

If a participant or participant's partner becomes or is found to be pregnant during the participant's treatment with the investigational product, the investigator must report this information to Pfizer Safety on the CT SAE Report Form and an EDP supplemental form, regardless of whether an SAE has occurred. In addition, the investigator must submit information regarding environmental exposure to a Pfizer product in a pregnant woman (eg, a participant reports that she is pregnant and has been exposed to a cytotoxic product by inhalation or spillage) to Pfizer Safety using the EDP supplemental form. This must be done irrespective of whether an AE has occurred and within 24 hours of awareness of the exposure. The information submitted should include the anticipated date of delivery (see below for information related to termination of pregnancy).

Follow-up is conducted to obtain general information on the pregnancy and its outcome for all EDP reports with an unknown outcome. The investigator will follow the pregnancy until completion (or until pregnancy termination) and notify Pfizer Safety of the outcome as a follow-up to the initial EDP supplemental form. In the case of a live birth, the structural integrity of the neonate can be assessed at the time of birth. In the event of a termination, the reason(s) for termination should be specified and, if clinically possible, the structural integrity of the terminated fetus should be assessed by gross visual inspection (unless preprocedure test findings are conclusive for a congenital anomaly and the findings are reported).

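### Pregnancy details are collected to about 130 days after the last dose but contraception is required for at least 154 days; both rest on drug elimination, and the nominal 24-day difference needs reconciling

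*Protocol*

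**What the plan says.** Three sections of the protocol set a period that runs from the last dose.

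- **Section 8.3.5.1 (Exposure During Pregnancy)** sets who is covered and from when: "Details of all pregnancies in female participants and, if indicated, female partners of male participants will be collected after the start of study intervention". Collection runs "until approximately 130 days that is at least 5 terminal half-lives after the last dose".
- **Section 10.4.2 (female participants, Appendix 4)** requires highly effective contraception in women of childbearing potential while they are on treatment. It then sets the period after dosing ends: "for at least 22 weeks after the last dose of study intervention, which corresponds to the time needed to eliminate any study intervention(s").
- **Section 10.4.1 (male participants, Appendix 4)** sets the same length on the same ground: "for at least 22 weeks after the last dose of study intervention, which corresponds to the time needed to eliminate study intervention(s").

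Section 4.2 says why this matters for this drug: "embryo-fetal developmental toxicology studies with PF-06946860 have not been conducted". It gives that as the reason for the contraceptive provisions.

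Scheduled contact ends earlier. Section 4.2 states: "After the 12-week treatment period, participants will be followed up for 12 weeks post last dose". The Schedule of Activities places the last dose at Week 12 (Day 85) and the last visit at Week 24 (Day 169), with contraception review and pregnancy testing at Weeks 15, 18 and 24.

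Two other places have no end date. Section 8.3.5 makes exposure during pregnancy reportable within 24 hours of the investigator becoming aware of it. The Appendix 4 text on collecting pregnancy information counts as exposure the case where "the female becomes or is found to be pregnant after discontinuing and/or being exposed to the investigational product". The specific reporting instruction that follows, however, is worded for a pregnancy that arises during the participant's treatment.

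**The concern.** The collection window and the contraception period serve linked purposes: one aims to prevent an exposed pregnancy, the other to record it if prevention fails. Both cover female participants and, through male participants, their partners. Both are justified by how long the drug stays in the body. One would expect collection to last at least as long as the protocol considers exposure possible. Here it stops sooner, and no reason is given.

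At stake is the completeness of pregnancy information for an antibody without embryo-fetal studies. Section 8.3.5.1 holds the only explicit end date for collecting pregnancy details, so a site can be expected to work to it. After Day 169 no visit or test would bring a pregnancy to light, and Section 8.3.1 does not oblige investigators to seek adverse events actively once participation has ended. The written window therefore carries the weight in exactly the interval where the two periods diverge.

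**Working it through.** **Inputs**

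| Quantity | Value | Source |
|---|---|---|
| End of pregnancy collection after last dose | about 130 days | Protocol 8.3.5.1 |
| Contraception after last dose | at least 22 weeks | Protocol 10.4.1, 10.4.2 |
| Nominal last dose | Day 85 | Schedule of Activities |
| Nominal last visit | Day 169 | Schedule of Activities |

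**Can the plan's figure be reproduced?** No. The 130 days is described as at least 5 terminal half-lives, but the clinical pharmacokinetic and dose-justification text is redacted and no half-life is visible. Only the two periods can be compared.

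**Step 1. Same unit.** 22 × 7 = 154 days. In weeks, 130 / 7 = 18.6.

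**Step 2. Difference.** 154 − 130 = 24 days, that is days 131 to 154 after the last dose.

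**Step 3. Relative size.** 24 / 154 = 15.6% of the post-dose contraception period. Contraception also applies during treatment: Day 1 to Day 85 adds 84 days, 84 + 154 = 238, and 24 / 238 = 10.1% of the whole period.

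**Step 4. Calendar.** Collection ends about Day 85 + 130 = Day 215. Contraception ends about Day 85 + 154 = Day 239, or later.

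**Step 5. Scheduled contact.** 169 − 85 = 84 days. That covers 84 / 130 = 65% of the collection window and 84 / 154 = 55% of the post-dose contraception period. After the last visit, 130 − 84 = 46 days of collection and 154 − 84 = 70 days of contraception remain.

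**Step 6. Half-lives, as an illustration only.** Assume each period is exactly 5 half-lives and that decline is simple and first-order.

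| Assumed half-life | 130 days is | Fraction left | 154 days is | Fraction left |
|---|---|---|---|---|
| 130 / 5 = 26.0 days | 5.0 half-lives | 3.1% | 5.9 half-lives | 1.6% |
| 154 / 5 = 30.8 days | 4.2 half-lives | 5.4% | 5.0 half-lives | 3.1% |

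At 26.0 days or shorter, the half-life statement in Section 8.3.5.1 is true and 22 weeks is simply longer. At 30.8 days, 130 days would fall short of the 5 half-lives that Section 8.3.5.1 claims. The documents do not say which case applies.

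**The case against.** The strongest reply is that the two statements need not conflict. Section 8.3.5.1 speaks of 5 half-lives; Appendix 4 speaks of elimination and names no multiple. With a half-life of 26 days both can be true, and the longer contraception period could include a margin. This stands in part: the documents do not establish that two different half-lives were used, or that either figure is wrong. But Appendix 4 states no margin and describes the whole 22 weeks as clearance time. On the protocol's own account, then, exposure is possible until at least day 154.

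A second reply is that both figures are hedged. That makes 24 days nominal, but does not close the gap: about 130 days does not stretch to 154, and a minimum of 22 weeks can only widen it.

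Three stronger readings are tempting, and the documents do not support them.

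- **A reader might infer that a pregnancy in the gap would be lost.** It would still be reportable once known, under Section 8.3.5 and the open-ended exposure definition in Appendix 4. The treatment-only wording of the Appendix 4 reporting instruction leaves some ambiguity, but nothing forbids a report.
- **A reader might infer that collection is the only protection, or that no visit covers either window.** Contraception is reviewed at clinic visits (Section 5.3.1), pregnancy is tested before dosing and through follow-up (Section 8.2.6), and intended or confirmed pregnancy ends dosing (Section 7.1.1). Visits cover the first 84 post-dose days; only the later part is without scheduled contact.
- **A reader might infer an oversight in Amendment 1.** The change log records "Updated contraception requirements per emerging PK data from C3651001" and lists no matching change to Section 8.3.5.1. That fits one section having been updated without the other, but does not prove it. The point rests on the current text alone.

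Finally, the study is small, with about 8 participants in each of at most two cohorts, all with advanced cancer, and no endpoint or analysis depends on these periods. That is correct and limits the weight of the point.

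**Conclusion.** The inconsistency holds. The current protocol ends planned collection of pregnancy details a nominal 24 days before it ends required contraception, while justifying both by elimination. That is about 16% of the post-dose contraception period, or about 10% if the treatment period is counted.

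The result assumes nominal visit days and takes 130 days and 22 weeks at face value. It does not depend on any half-life: 26.0 and 30.8 days follow only if each period is exactly 5 half-lives.

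The consequence is limited to planned collection of safety information. Few events would be expected at this sample size, and no estimate is affected. It still merits correction before the protocol is relied on further, because embryo-fetal studies had not been done and the affected days fall after the last scheduled contact. The documents do not show which duration is right.

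**What to change.** Reconcile Section 8.3.5.1 with Sections 10.4.1 and 10.4.2. State one elimination basis, including the half-life or multiple it uses, and express both periods relative to it so that they either agree or differ for a stated reason. In the same edit, make the Appendix 4 reporting instruction consistent with its own definition, which already reaches past the end of dosing. Check that the consent form matches.

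The choice of duration belongs to the sponsor's clinical pharmacology and safety functions. The cost is protocol wording and a consent-form check; no extra visit, sample or analysis is needed.

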#### **8.3.5.2. Exposure During Breastfeeding**

Scenarios of exposure during breastfeeding must be reported, irrespective of the presence of an associated SAE, to Pfizer Safety within 24 hours of the investigator's awareness, using the CT SAE Report Form. An exposure during breastfeeding report is not created when a Pfizer drug specifically approved for use in breastfeeding women (eg, vitamins) is administered in accord with authorized use. However, if the infant experiences an SAE associated with such a drug's administration, the SAE is reported together with the exposure during breastfeeding.

#### **8.3.5.3. Occupational Exposure**

An occupational exposure occurs when, during the performance of job duties, a person (whether a healthcare professional or otherwise) gets in unplanned direct contact with the product, which may or may not lead to the occurrence of an AE.

An occupational exposure is reported to Pfizer Safety within 24 hours of the investigator's awareness, using the CT SAE Report Form, regardless of whether there is an associated SAE. Since the information does not pertain to a participant enrolled in the study, the information is not recorded on a CRF; however, a copy of the completed CT SAE Report Form is maintained in the investigator site file.

### **8.3.6. Cardiovascular and Death Events**

Not applicable.

### **8.3.7. Disease-Related Events and/or Disease-Related Outcomes Not Qualifying as AEs or SAEs**

Not applicable.

### **8.3.8. Adverse Events of Special Interest**

All AESIs must be reported as an AE or SAE following the procedures described in [Sections 8.3.1](#) through [8.3.4](#). An AESI is to be recorded as an AE or SAE on the CRF. In addition, an AESI that is also an SAE must be reported using the CT SAE Report Form.

#### **8.3.8.1. Lack of Efficacy**

Lack of efficacy is reportable to Pfizer Safety only if associated with an SAE.

### **8.3.9. Medical Device Deficiencies**

Not applicable.

### **8.3.10. Medication Errors**

Medication errors may result from the administration or consumption of the investigational product by the wrong participant, or at the wrong time, or at the wrong dosage strength.

Exposures to the investigational product under study may occur in clinical trial settings, such as medication errors.

Safety Event	Recorded on the CRF	Reported on the CT SAE Report Form to Pfizer Safety Within 24 Hours of Awareness
Medication errors	All (regardless of whether associated with an AE)	Only if associated with an SAE

Medication errors include:

- Medication errors involving participant exposure to the investigational product;
- Potential medication errors or uses outside of what is foreseen in the protocol that do or do not involve the study participant.

Such medication errors occurring to a study participant are to be captured on the medication error page of the CRF, which is a specific version of the AE page.

In the event of a medication dosing error, the sponsor should be notified within 24 hours.

Whether or not the medication error is accompanied by an AE, as determined by the investigator, the medication error is recorded on the medication error page of the CRF and, if applicable, any associated AE(s), serious and nonserious, are recorded on an AE page of the CRF.

Medication errors should be reported to Pfizer Safety within 24 hours on a CT SAE Report Form **only when associated with an SAE**.

